4. OBJECTIVE(S)/SPECIFIC AIMS AND HYPOTHESES

- *A concise statement of the goal(s) of the current study.*
- *The rationale for and specific objectives of the study.*
- *The goals and the hypothesis to be tested should be stated.*

1. To determine if IRIS facilitates interpretation of VLE images compared to VLE alone
2. To determine if IRIS increases the diagnostic yield for dysplasia compared to VLE alone and random biopsies
3. To determine if IRIS decreases the number of biopsies needed to identify dysplasia compared to VLE alone and random biopsies |

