8. NUMBER OF SUBJECTS

- *Indicate the total number of subjects to be accrued locally. If applicable, distinguish between the number of subjects who are expected to be pre-screened, enrolled (consent obtained), randomized and complete the research procedures.*
- *If your study includes different cohorts, include the total number of subjects in each cohort.*
- *If this is multisite study, include total number of subjects across all sites.*

This is a multi-site randomized trial with an anticipated enrollment of 200 patients. We anticipate adding up to 3 other sites. Half of all patients should have a prior diagnosis of dysplasia to ensure a sample that has an adequate number of dysplastic patients.

The primary outcome will be time to interpretation of a VLE scan with and without IRIS. Dysplasia detected in each arm and number of biopsies are secondary outcomes and not expected to be that much different as expert VLE users will be involved in the study. The expected mean time for a VLE without IRIS is 5 min +/- 3 min. The mean time for a VLE without IRIS (standard) is 3 min. With a CI of 95% and power of 90%, the sample size for 1:1 randomization is 94 (47 in each group). Our sample size is 200 to allow for screen failures.

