10. ENDPOINTS

- *Describe the primary and secondary study endpoints*
- *Describe any primary or secondary safety endpoints*

The following outcomes will be measured:

- Primary Outcome: The time for image interpretation in each arm will be compared. Time will be a surrogate for ease of interpretation. Time will be recorded from start of image interpretation to the end of image interpretation. Length of Barrett's will be taken into account (time per cm of Barrett's) when comparing this outcome between patients and procedures.
- Secondary Outcome: Biopsy yield of dysplasia/diagnosis of dysplasia (dysplasia present versus not) of IRIS biopsies (double laser mark) will be compared to VLE without IRIS biopsies (single laser mark) and random biopsies.
- Secondary Outcome: The number of biopsies will be compared among all groups. |

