11. RESEARCH PROCEDURES

- *Include a detailed description of all procedures to be performed on the research subject and the schedule for each procedure.*
- *Include any screening procedures for eligibility and/or baseline diagnostic tests*
- *Include procedures being performed to monitor subjects for safety or minimize risks*
- *Include information about drug washout periods*
- *If drugs or biologics are being administered provide information on dosing and route of administration*
- *Clearly indicate which procedures are only being conducted for research purposes.*
- *If any specimens will be used for this research, explain whether they are being collected specifically for research purposes.*
- *Describe any source records that will be used to collect data about subjects*
- *Indicate the data to be collected, including long term follow-up*

This is a prospective randomized clinical trial examining how IRIS (Intelligent Real-time Image Segmentation) affects biopsy patterns in VLE (Volumetric laser endomicroscopy). Patients will undergo a VLE exam with and without IRIS per the standard of care. All patients regardless of the study participation in this study would receive VLE with and without IRIS clinically. Thus randomization into a particular order will not require more procedure time. They will be randomized into VLE without IRIS first vs VLE with IRIS first. Subjects will be randomized with the BUDDY Randomization System provided for use by the Northwell Health Biostatistics Unit. Randomization will occur before the procedure starts. Randomization will be stratified based on prior diagnosis of dysplasia. The order the patient is randomized to will be recorded on the case report form. There will be concealed allocation as the study coordinator performing the randomization will not know the order of the next allocation.

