Both VLE and IRIS imaging are being performed as standard of care. However, randomization of the order allows for comparison of the two. Regions of interest (ROI) will be recorded using a full scan and recorded on the case report form. The time to identification of ROIs will also be recorded (from start of image interpretation to the end). Each group will then cross over such that the VLE without IRIS group will then have IRIS turned on ROI will then be recorded for each group based on full scans. A consensus ROI will be recorded based on the two exams. Only one ROI per centimeter will be allowed to avoid overlapping of laser marks. In addition VLE without IRIS and IRIS marks within 75 frames of each other or 2 hours (on a clock face orientation) will be considered the same target.

Laser marking will then be performed. A double laser mark will be applied to all IRIS ROIs. A single laser mark will be applied to VLE ROIs. Targeted biopsies will be taken of all laser marks and placed in separate biopsy jars. Biopsies will be taken in between the laser marks for double laser marked areas. For single laser marks, biopsies will be taken on either side of the laser mark. Resection of visible

lesions will then occur per standard of care (if present) followed by random biopsies of the segment. Random biopsies are pinch biopsies every 1 cm the length of the Barrett's in a 4 quadrant fashion per gastrointestinal society guidelines. This is all per standard of care. There are no additional research biopsies being performed outside this study. The targeted biopsies are based on the VLE features that are suspicious for dysplasia and thus standard of care. The other biopsies being performed here are random biopsies which are also being performed for standard of care. Biopsied samples will be stored per standard of care procedures per the pathology department. They will not be stored for future research purposes.

Following each procedure, the physician will be asked a series of Likert Scale questions to assess the utility of IRIS in that procedure, including how it impacts their confidence in image interpretation, their ability to assimilate data more easily and quickly, and their overall perception of the technology.

Although the VLE with IRIS and VLE without IRIS are being performed as standard of care, all adverse events will be recorded and reported to the IRB.

All data will be entered into a central encrypted REDCap database housed within the Northwell server.

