12. STATISTICAL ANALYSIS

- *Describe how your data will be used to test the hypotheses.*
- *State clearly what variables will be tested and what statistical tests will be used.*
- *Include sample size calculations.*
- *If this is a pilot study, state which variables will be examined for hypothesis generation in later studies.*

The categorical variables will be compared using Fisher exact tests (eg: presence of dysplasia). Continuous variables between the two groups will be analyzed using the student t-test. All statistical tests will be 2-sided, and $P < .05$ will be considered significant. All statistics will be run using SAS version 9.4 (SAS Institute Inc, Cary, NC, USA).

Time to interpretation is likely normally distributed. For outcomes like number of biopsies, if post study analysis shows this is not normally distributed, we can use median values instead of means or perform a log correction.

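### The secondary dysplasia and biopsy-count outcomes are worded by undefined 'arm' in section 8 and by biopsy source in section 10, and section 12's independent two-group tests suit neither reading

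*Combined protocol and SAP*

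**What the plan says.** - **Section 8 (Number of Subjects):** "Dysplasia detected in each arm and number of biopsies are secondary outcomes and not expected to be that much different". The sentence goes on to give the involvement of expert VLE users as the reason. 'Arm' is not defined there or elsewhere.
- **Section 10 (Endpoints):** dysplasia yield "of IRIS biopsies (double laser mark) will be compared to VLE without IRIS biopsies (single laser mark) and random biopsies". For biopsy number: "The number of biopsies will be compared among all groups".
- **Section 4 (Objectives), second aim:** "To determine if IRIS increases the diagnostic yield for dysplasia compared to VLE alone and random biopsies". The third aim asks the same contrast for the number of biopsies needed.
- **Section 11 (Research Procedures), what is randomized:** "They will be randomized into VLE without IRIS first vs VLE with IRIS first". What every patient receives: "Patients will undergo a VLE exam with and without IRIS per the standard of care". Before any laser marking: "Each group will then cross over such that the VLE without IRIS group will then have IRIS turned on". All laser marks are then biopsied into separate jars, and random biopsies follow.
- **Section 12 (Statistical Analysis):** "Continuous variables between the two groups will be analyzed using the student t-test". Categorical variables, with presence of dysplasia as the example, get Fisher exact tests. No paired method is named.

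**The concern.** The same two secondary outcomes are described in terms that need not mean the same thing, and the section that names the tests does not settle which is intended. Only reading order is randomized, so an analyst working from sections 8 and 12 could reasonably take the two groups to be the two orders. Section 11 itself uses 'group' in that sense when it describes the crossover. That analysis would not answer objectives 2 and 3. Because section 8 already expects little difference, a null result that came from the choice of contrast could be taken as confirmation.

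An analyst working from section 10 would have the right contrast but would find only independent-sample tests for data in which each patient contributes to every source.

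**Working it through.** **The plan's own figure.** The only sample size in the documents is for reading time. With a difference of 5 − 3 = 2 min, SD 3, two-sided 0.05 and 90% power: 2 × [3 × (1.960 + 1.282) / 2]² = 47.3 per group, against the stated 47 (94 in total). It reproduces to rounding and does not bear on this point. The documents give no detection rates for dysplasia, so every rate below is an assumption.

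**Reading A: 'arm' is reading order, and all of a patient's biopsies count.** Let v and i be the per-patient probabilities that VLE-alone targets and IRIS targets yield dysplasia. In both orders both reads are done and all marks are biopsied. Taking the two detections as independent, the pooled rate is 1 − (1 − v)(1 − i) in each order. With no order effect the expected difference is zero for any v and i. Fisher exact, 100 per order, two-sided 0.05, 4,000 simulated trials:

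| VLE v | IRIS i | Pooled rate, each order | Rejection |
|---|---|---|---|
| 10% | 20% | 28% | 3.0% |
| 15% | 30% | 40.5% | 4.0% |
| 20% | 40% | 52% | 3.8% |

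IRIS doubles detection in every row, yet the test rejects no more often than its nominal level. Random biopsies are also taken in both orders, so adding them does not separate the orders. Total biopsies per order behave in the same way, being the sum over all sources.

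**Reading A, first-read targets only.** If only targets from the first read counted, the orders would differ in display. The same three rows then give 43%, 67% and 85% power. No section specifies such an analysis.

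**Reading B: 'arm' is display or source.** Each patient now supplies an IRIS result and a VLE result, so the information lies in the discordant patients. McNemar exact, two-sided 0.05, 200 patients:

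| IRIS only | VLE only | Power |
|---|---|---|
| 4% | 2% | about 13% |
| 5% | 2% | about 27% |
| 10% | 5% | about 37% |
| 12% | 2% | about 97% |

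**Reading B with section 12's test.** Take the last row with a further 18% of patients detected by both. The marginal rates are 18 + 12 = 30% for IRIS and 18 + 2 = 20% for VLE. Unpaired Fisher on 200 against 200 rejects in about 66% of trials, against about 97% for McNemar on the same patients. The gap of about 31 points is the cost of ignoring the pairing in that scenario.

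**Reading A on those same rates.** If random biopsies add nothing, the pooled rate is 18 + 12 + 2 = 32% in both orders, and Fisher rejects in about 3.5%. First-read targets only (30% v 20%, 100 per order) would give about 31%.

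**Shared targets.** Section 11 treats nearby IRIS and VLE marks as one target and gives every IRIS region a double mark. If shared targets were credited to IRIS alone, then at the extreme, where all of the 18% arise from shared targets, the split would move from 12% v 2% to 30% v 2% with no change in what either read found. The crediting rule therefore has to be stated.

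**The case against.** The best reply is that 'arm' in section 8 is a loose word for display condition. The sentence before it frames the primary outcome as reading with and without IRIS, and section 10 describes that same outcome as time in each arm. The reason given for expecting little difference, expert readers, makes sense for IRIS against no IRIS and explains nothing about two reading orders. Section 10 is the endpoint section, its definition is operational, and it matches the objectives and the separate jars. In section 12 the two-group phrase is attached to continuous variables; the Fisher sentence names no groups.

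Most of this stands, and it rules out three stronger inferences that a reader might draw:

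- That the plan defines dysplasia by randomized arm and is therefore null by construction. Section 8 never says randomized arm, and the null applies only to the pooled by-order comparison without order effects.
- That the random-biopsy comparison is lost. Sections 4 and 10 both keep it.
- That choosing between the plan's two wordings moves power from about 3% to about 97%. The 97% needs McNemar, which the plan does not name, and an assumed 12% v 2% split that sits badly with section 8's expectation of little difference. It also uses all 200 patients, a number that includes an allowance for screen failures; at 94 patients the same split gives about 70%.

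The reply does not rescue section 12. If 'arm' means display, the comparison is within patient and the named tests are still the wrong ones. Section 12's fallback for biopsy number, medians or a log transformation, deals with skewness and not with pairing.

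**Conclusion.** The point holds as an ambiguity with a consequence under either reading. By reading order over all biopsies, the comparison carries no IRIS signal: rejection is about 3-4% under the assumed rates, and any true difference would be an order effect. By display or source, the comparison is the intended one, but independent-sample tests ignore the pairing; in the one scenario worked through, that lowers power from about 97% to about 66%. Paired power itself runs from about 13% to 97% over the assumed discordant rates, so no single figure should be quoted. The size of the problem rests on those assumptions. The mismatch between the contrast and the tests does not. The primary outcome's sample size is unaffected.

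**What to change.** 1. **Section 8:** replace the by-arm phrase with dysplasia detected, and number of biopsies, by biopsy source as defined in section 10. Define 'arm' and 'group' once and use them consistently.
2. **Section 12:** state that these outcomes are compared by source within patient with paired methods, for example McNemar exact for dysplasia present or absent per patient, and a paired t-test or signed-rank test for biopsy counts. State that randomized order enters only as a factor for order effects.
3. **Shared targets:** state how a target found on both reads is credited, for example to both IRIS and VLE.
4. **Power:** if any is quoted for the dysplasia outcome, give it as a range over stated discordant rates.

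The cost is wording in sections 8 and 12. Regions of interest are already recorded for each read and the laser-mark biopsies already go into separate jars, so no new data or patients are needed.

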Volumetric laser endomicroscopy (VLE) procedures use an advanced imaging technology that became commercially available in the United States in 2013 (NvisionVLE® imaging System, NinePoint Medical Inc., Bedford, MA). The VLE procedure uses an FDA-cleared second-generation optical coherence tomography (OCT) technology. It uses infrared light to produce real time high-resolution cross sectional imaging of the esophagus. The NvisionVLE system can scan a 6 cm length of the esophagus in approximately 90 seconds, providing surface and subsurface wide-field cross-sectional imaging with an axial resolution of 7 μ m, and to a depth of 3 mm.[8,9] The VLE imaging system consists of a console, monitor, and optical probe contained within a Mylar balloon on an 8Fr, 260 cm catheter. The distal end of the catheter connects to the console. The probe is available in 14 mm, 17 mm, and 20 mm diameter balloons that are 6 cm in length. The balloon is positioned such that the distal margin of the balloon is located 1 cm distal to the gastroesophageal junction. This allows a single scan to image the gastric cardia, the gastro-esophageal (GE) junction, and the distal esophagus. The balloon is inflated to 15 psi, though depending on anatomy the balloon inflation pressure may be modified accordingly. The inflated balloon allows for centering and anchoring of the probe while helical scanning occurs. Imaging is performed during automatic retraction of the probe from the distal to proximal end of the balloon over a 90 second period, creating real time 360-degree images. Twelve hundred cross sectional scans are generated over the 6 cm segment. VLE scans are viewed by using a software interface that allows real time viewing of cross-sectional, transverse, and longitudinal views. There is a registration line on the balloon and

the VLE images that allows for orientation of VLE images with endoscopic imaging.

A recent upgrade to the imaging platform includes the ability to perform superficial laser marking of the esophageal epithelium when suspicious areas are identified on VLE to provide more precise targeting for biopsies or endoscopic resection .[10] A safety and efficacy study was performed evaluating VLE with a prototype laser marking device in 16 BE patients with 222 laser marks placed.[11] The study showed that laser marking was safe and efficacious with an 85% positional accuracy rate of the laser marks.

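### Section 8 labels both planning means as without IRIS and powers the trial in raw minutes, so the stated 90% is not established for the time-per-cm primary endpoint; which reads are compared also needs one sentence.

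*Combined protocol and SAP*

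**What the plan says.** Section 8 states the planning assumptions in two consecutive sentences: "The expected mean time for a VLE without IRIS is 5 min +/- 3 min" and "The mean time for a VLE without IRIS (standard) is 3 min". From these, with 95% confidence and 90% power, it concludes that "the sample size for 1:1 randomization is 94 (47 in each group", and it sets enrollment at 200 to cover screen failures.

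Section 10 makes interpretation time the primary outcome and compares it by arm. It adds that Barrett's length "will be taken into account (time per cm of" Barrett's) "when comparing this outcome between patients and procedures".

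Section 11 randomizes only the order of the two readings, and every patient is read with and without IRIS. "Randomization will be stratified based on prior diagnosis of dysplasia". It also says that "Regions of interest (ROI) will be recorded using a full scan". Reading time is described before the crossover; after the crossover only the recording of ROIs is mentioned. The same section says that randomizing the order is what permits the two methods to be compared.

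Section 12 names a two-sided Student t-test between two groups for continuous variables. It has no paired, period or stratum term.

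Section 3 describes the scan: "Twelve hundred cross sectional scans are generated over the 6 cm segment", with the balloon's distal edge 1 cm beyond the gastroesophageal junction. Section 7 admits any Barrett's length above 2 cm.

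**The concern.** Three things do not line up.

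- **Labels.** One of the two means is presumably the with-IRIS value, but the text does not show which. The word marking the standard method sits on the 3 min figure. Taken literally, that makes IRIS the slower condition, against the first aim in section 4.
- **Scale.** The calculation is in minutes and the endpoint is in minutes per cm. Power carries over only under some relation between reading time and length. Each scan has a fixed number of frames over 6 cm and ROIs come from the full scan, so reading time need not be proportional to Barrett's length. Where it is not, dividing by length adds noise.
- **Reads.** Each patient could supply two reading times. Comparing first reads between orders and comparing both reads within patients are different analyses, and the second read follows a first look at the same segment.

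At stake are a power statement that does not describe the primary endpoint, and a primary comparison that is not fully fixed before the data are seen.

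**Working it through.** **1. The plan's own figure.** Inputs from section 8: means 5 and 3 min (difference 2), SD 3, power 90%, 1:1 allocation. Two-sided 5% comes from section 12. The SD is attached to only one mean; applying it to both is an inference.

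n per group = 2 × (1.960 + 1.282)² × 3² / 2² = 47.3

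This rounds to 47, or 94 in total. Exact noncentral-t power is 89.2% at 47 per group and 99.7% at 100. One-sided testing would give 39 per group and 80% power would give 36, so the plan's figure is the two-sided, independent-groups calculation in raw minutes. Swapping the labels changes the sign of the difference but not n.

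**2. The per-cm scale.** No per-cm mean or SD is given, so the values below are simulated under assumptions: first reads only, lognormal times with means 5 and 3 min and SD 3 in both arms, and a t-test on min/cm.

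| Assumed lengths | Assumed relation of time to length | Power, 47 per group | Power, 100 per group |
|---|---|---|---|
| Uniform 2–6 cm | Unrelated | 81% | 97% |
| Uniform 2–6 cm | Partly scales (square root) | 88% | 99% |
| Uniform 2–6 cm | Proportional | 92% | >99% |
| Uniform 2–10 cm | Proportional to number of scans needed | about 90% | about 99% |

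The last row uses 5 or 6 cm of coverage per scan; both give about 90%. In the 2–6 cm rows, the implied per-cm mean/SD runs from 1.37/0.98 against 0.82/0.90 (unrelated) to 1.25/0.63 against 0.75/0.69 (proportional). If the SD fell with the mean (3 and 1.8 min), simulated power at 47 per group would be 85% or more.

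**3. How many are randomized.** The 200 includes an allowance for screen failures, with no rate given. Falling from 200 to 94 would be a loss of 1 − 94/200 = 53%. The number per group is therefore at most 100.

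**4. Which reads.** Pointing to first reads between randomized orders: the comparison by arm in section 10, the group sizes in section 8, the two-group test in section 12, and the timing described before the crossover in section 11. Leaving both reads possible: the word procedures in "when comparing this outcome between patients and procedures", and the section 11 remark that randomizing the order permits the comparison of the two methods.

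**5. If both reads entered the section 12 t-test.** With equal variances and within-patient correlation rho (assumed; the documents give none):

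- real alpha = 2 × [1 − Φ(1.96 / √(1 − rho))]
- interval width relative to a paired analysis = 1 / √(1 − rho)

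| rho | Real alpha | Width ratio |
|---|---|---|
| 0.3 | 1.9% | 1.20 |
| 0.5 | 0.6% | 1.41 |
| 0.7 | 0.03% | 1.83 |

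The error is in the conservative direction.

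**The case against.** The strongest reply is that nothing is lost in practice. The label slip leaves the two-sided sample size alone, and the first aim suggests which value was meant for IRIS. First reads are the natural reading; if time is captured only once per patient, there is only one comparison to make. With up to 200 patients, power is ample on either scale.

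Much of this stands. First reads are the better-supported reading, and the flow diagram and case report form, which might show whether the second read is timed, are not available here. The power range also rests on lengths, distributions and time–length relations that the documents do not supply.

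A reader might go further and infer that the trial is underpowered. Pairing lengths of 2–10 cm with a reading time that does not grow with length gives 74% at 47 per group. Section 3 does not support that pairing: one scan covers 6 cm, so a 10 cm segment needs at least two scans. With time proportional to scans needed, power returns to about 90%.

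A reader might also infer that ignoring pairing would inflate false positives; step 5 of the working shows the reverse. Nor do the documents show that min/cm is the wrong scale. When time is proportional to length it has slightly more power than length-adjusted minutes (92.2% against 90.6% at 47 per group, lengths 2–6 cm).

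The reply does not remove the mislabelled mean, the absence of any per-cm planning value, or the missing sentence on which reads are compared.

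**Conclusion.** The concern holds in a limited form. Section 8 states no with-IRIS planning value, and its 90% applies to two independent groups in raw minutes, not to the section 10 endpoint. Under the scenarios tabulated (SD 3 in both arms), per-cm power at 47 per group is about 81% to 92%, so the stated 90% may be somewhat optimistic or slightly pessimistic. At 100 per group it is about 97% or more, so no shortfall is shown there for a 2 min difference; 100 per group is an upper bound.

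The text leans towards first reads but leaves both reads open. Pooling both in the unpaired test would cost precision without adding false positives. Confidence is high on labels and scale, and moderate on the reads because the flow diagram and case report form are not shown. This should be corrected before analysis; it does not invalidate the trial.

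**What to change.** 1. In section 8, correct the labels so that one mean is with IRIS and the other without, and state the SD assumed for each.
2. In section 12, state that the primary comparison is first reads between the two randomized orders, on the section 10 scale (min/cm), adjusted for the stratification factor, prior dysplasia. Give minutes adjusted for Barrett's length as a supporting analysis. If the sponsor intends both reads, confirm that both are timed, replace the unpaired t-test with a paired or mixed model with a period term, and report first reads as a sensitivity analysis.
3. Restate power in min/cm at the number expected to be randomized, giving the assumed per-cm SD with a range and, if both reads are used, a range for the within-patient correlation.

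The cost is text in sections 8 and 12, with no added enrollment. First reads need no change in procedures. Using both reads may need a second timing field on the case report form and relies on similar carry-over in the two orders. The restated power will still rest on assumed inputs, which should be labelled as such.
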